8.6 STATISTICAL METHODS

Non-inferential analysis will be performed due to the safety nature of the study. The following sections refer to descriptive statistics for the different variables of section 8.4.

All analyses will be performed using Safety set.

8.6.1 General Descriptive Analysis

The results will be presented of standard methods¹⁸:

- Continuous variables: Mean, 95%CI of Mean (95% mean confidence interval), SD (standard deviation), minimum, P25 (percentile 25), Median, P75 (percentile 75), maximum and N.
- Categorical variables: total frequency and percentages and for each category.
- Ordinal variables with few categories (less than 10) will be described using two tables: one including continuous variables descriptive parameters (as long as the interpretation is reasonable) and the other including categorical variables descriptive parameters. For ordinal variables with >10 categories, the same approximation used for continuous variables will be applied.

Where applicable, these summaries will be provided by time-point (scheduled time-point) including the absolute differences from baseline. The data of unscheduled time-points will be only listed. Additionally, only for the size of tumor the relative difference from baseline will be also described.

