7. STUDY PROCEDURES

7.1 FLOW CHART/TIME AND EVENTS SCHEDULE

| | |
|--|---|
| | 
confirm all the inclusion and exclusion criteria to receive cabozantinib.
 
• Respect the 15 days of first-line treatment washout before starting cabozantinib.• Chest and abdominal CT scan within 4 weeks before starting therapy.• Liver biopsy within 4 weeks before starting therapy. |
| | 
Drug administration
 
Cabozantinib will be given orally every day. All patients will start with 60 mg/day to be modified upon development of adverse events.
 |
| | 
Clinical evaluation at day 1 of every cycle and at day 15 of cycle 1 and 2.
 
Unscheduled visits will be made should they be needed (adverse events or symptoms).
 |
| | 
Laboratory evaluation at day 1 of every cycle and at day 15 of cycle 1 and 2.
 
Unscheduled laboratory evaluation will be made should they be needed (adverse events or symptoms).
 |
| | 
Radiological tumor evaluation at tumor evaluation at week 8 according to the RECIST criteria v1.1
 |
| | 
Dose modifications:
 
Cabozantinib dose will be modified according to the manufacturer's recommendations.
 |

| |
|---|
| 
Serum biomarker determination:
 
At baseline and at each time point accordingly to table 5, serum biomarker will be evaluated.
 |
| 
Liver biopsy will be done if the patient develops radiologic tumor progression, performance status 0/1 and preserved liver function.
 
Patients with symptomatic tumor progression will not be biopsied.
 
All patients on must stop cabozantinib 5-7 days before performing the biopsy to avoid the risk of bleeding. They will be visited 5-7 days after the biopsy to re-start cabozantinib.
 |
| 
Patient-reported Quality of Life Questionnaires:
 
The FACT-Hep (Version 4), EORTC- QLQ C30, EORTC-HCC18 and the EQ-5D should be self-administered by the subject at the start of the visit, before the subject sees the investigator and before any study related procedures are done, so that any interaction between the patients and investigator or other health care provider will not influence the responses to the questionnaires. Questionnaires should be administered at Day 1 of Cycle 1 and Cycle 3, then at Day 1 every 3 cycles and at the End of Treatment (EOT) visit. The site personnel should complete the Patient Reported Outcomes Information Sheet.
 |

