7.2 SAFETY ASSESSMENTS

7.2.1 ASSESSMENTS AND DOCUMENTATION OF ADVERSE EVENTS

All AEs occurring after the subject has signed the informed consent form (IC) up until the end of the safety follow-up period (30 ± 7 days after permanently discontinuing cabozantinib administration) must be fully recorded in the subject's CRF.

Adverse event documentation is event-based (using the NCI-CTCAE version 5.0 guidelines). Adverse events should be collected past 30 days after the study treatment stop for all AEs that were ongoing at the end of treatment as well as new adverse events that in the opinion of the investigator could be related to study treatment. (Information may be obtained via phone call).

Documentation must be supported by an entry in the subject's file.

Adverse events should be followed until resolution or stabilization unless, in the investigator's opinion, the condition is unlikely to resolve due to the patient's underlying disease.

If any patient dies within 30 days of last dose of study drug, the investigator will inform the sponsor and record the cause of death in detail within 24 hours on a SAE form.

A laboratory test abnormality considered clinically relevant, e.g. causing the subject to withdraw from the study, requiring treatment or causing apparent clinical manifestations, or judged relevant by the investigator, should be reported as an AE. Each event should be described in detail along with start and stop dates, severity, relationship to investigational product, action taken and outcome.

Note that all the patients will receive the "alert card" reporting useful information in case of need such as the name of the clinical trial, the name and contacts of PI or collaborators.

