7.2.3 INVESTIGATOR'S NOTIFICATION TO THE SPONSOR

All investigators will be thoroughly instructed and trained on all relevant aspects of the investigator's reporting obligations for SAEs. This information, including all relevant contact details, is summarized in the investigator site file. This information will be updated as needed.

All SAEs occurring during the observation period defined in [Section 8.2](#) must immediately (within 24 hours of the investigator's awareness) be reported to the recipient detailed in the manual. A SAE form must also be completed within 24 hours of the investigator awareness and forwarded to the designated recipient. Each SAE must be followed up until resolution or stabilization by submission of updated reports to the designated recipient.

In each case of a fatal or life-threatening reaction, the investigator must seek relevant follow-up information and must complete a follow-up report to be faxed to the sponsor as soon as possible but not later than 8 calendar days after the initial report is sent.

An isolated laboratory abnormality that is assigned Grade 4, according to CTCAE v.5.0 definition, is not reportable as an SAE, unless the investigator assesses that the event meets standard International Conference on Harmonization (ICH) criteria for an SAE. CTC Grade 4 baseline laboratory abnormalities that are part of the disease profile should not be reported as an SAE, specifically when they are allowed or not excluded by the protocol inclusion/exclusion criteria. If an investigator is in doubt about the applicable reporting obligations, he/she should consult with the study monitor for the Sponsor. CTC Grade 4 lab abnormalities will be documented in the laboratory data and will be reviewed on a regular basis.

For all SAEs, the investigator is required to document in full, the course of the SAE and any therapy given, including any relevant findings/records in the report.

It is not mandatory to report SAEs occurring after the protocol-defined observation period, however, at the investigator's discretion these may be reported if considered potentially relevant. In such cases, the SAEs will be processed by the sponsor according to all applicable regulations.

Notification to the IECs / IRBs

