8.1.1 ADVERSE EVENT (AE)

An AE is any untoward medical occurrence in a patient or clinical investigation subject administered a medicinal product and that does not necessarily have a causal relationship with this treatment. An AE can therefore be the development of a new medical condition, or the deterioration of a pre-existing medical condition. This includes any unfavorable and unintended sign (e.g. tachycardia, enlarged liver), symptom (e.g. nausea, chest pain) or the abnormal results of an investigation (e.g. laboratory findings, electrocardiogram) temporally associated with the use of a medicinal product, whether or not considered related.

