8.6.5.3 Other variables

A descriptive analysis will be performed for all variables of section 8.4.2 with the appropriate descriptive statistics (see section 8.6.1).

The continuous variables (laboratory parameters, vital signs and other continuous variables included in section 8.4.2) recruited by time (absolute values and absolute differences when applicable) will be analyzed by means of MMRM model specified in section 8.6.2. The same model with previous rank transformation will be applied to ordinal variables.

These analyses will be performed using Safety set on ADO approach.

The following sections describe the specific statistical analysis.

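### Grade 3-4 laboratory toxicity is counted only if it is reported as an AE: the SAP derives no CTCAE grades from laboratory values and keeps unscheduled values out of its summaries

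*SAP*

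**What the plan says.** **Summaries.** Under SAP 8.6.1, "these summaries will be provided by time-point (scheduled time-point) including the absolute differences from baseline". The next sentence deals with everything else: "The data of unscheduled time-points will be only listed".

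**Laboratory analysis.** SAP 8.6.5.3 applies the 8.6.1 descriptive statistics to all variables in SAP 8.4.2. It adds a repeated-measures mixed model for "The continuous variables (laboratory parameters, vital signs and other continuous variables included in section 8.4.2) recruited by time". The outputs are Table 22 (vital signs), Tables 23-27 (laboratory) and laboratory Listings 17-21. None mentions a CTCAE grade, a worst value or a shift from baseline.

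**Unscheduled tests.** Protocol 7.1: "Unscheduled laboratory evaluation will be made should they be needed (adverse events or symptoms".

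**When a laboratory result is an AE.** Protocol 7.2.1 covers "A laboratory test abnormality considered clinically relevant, e.g. causing the subject to withdraw from the study, requiring treatment or causing apparent clinical manifestations", and continues "or judged relevant by the investigator, should be reported as an AE". The synopsis has the same rule. Protocol 8.1.1 defines an AE to include "the abnormal results of an investigation (e.g. laboratory findings, electrocardiogram", with no relevance condition.

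**Primary outcome.** The rate that drives the sample size counts AEs of grade 3 or higher other than palmar-plantar erythrodysesthesia (SAP 7.4, 8.3.1, 8.6.5.1). Table 56, the output by CTCAE grade, counts reported AEs.

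**The concern.** This is an open-label, single-arm trial whose stated main purpose is safety. Its key numerator is built from investigator-reported AEs. Laboratory values are the one objective source against which that reporting could be checked. The plan uses them only as ungraded continuous variables at scheduled visits, and moves to listings the values drawn because something seemed wrong.

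The protocol itself foresees grade 3-4 laboratory results that may not count as clinically relevant. Table 2 (section 6.1.4.1) makes an exception for clinically non-relevant laboratory abnormalities at grade 3 and at grade 4. Section 6.1.6 treats several asymptomatic grade 4 laboratory findings separately. For such results, withdrawal, treatment or manifestations may not arise, which leaves investigator judgement. Two AE definitions that differ on this point, applied at seven sites, could produce uneven reporting that no planned table would show.

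**Working it through.** **1. Route of a grade 3-4 laboratory value into the results**

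| Value | Where it appears | Graded? | Gives a count of affected patients? |
|---|---|---|---|
| Reported as an AE | Primary outcome, Tables 9 and 47-56 | Yes | Yes |
| Not reported, scheduled visit | Tables 23-27 (minimum, quartiles, maximum, mean, model estimate) and Listings 17-21 | No | No |
| Not reported, unscheduled | Listings only | No | No |

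Only the first row yields a toxicity rate. Entry to it depends on whether Protocol 7.2.1 or 8.1.1 is followed.

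**2. The plan's own design figure**

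The inputs from SAP 7.4 are a null rate of 56%, an alternative of 32.5%, 14 + 26 = 40 patients, one-sided alpha of 2.5% and power of 80%. Let p be the critical-AE rate. The trial continues if at most c1 of 14 patients have an event, and rejects the null if at most c of 40 do:

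P(reject) = Σ(x = 0..c1) C(14,x) p^x (1−p)^(14−x) × Σ(y = 0..c−x) C(26,y) p^y (1−p)^(26−y)

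- c1 = 6, c = 16: 0.0239 at p = 0.56 and 0.8004 at p = 0.325. This reproduces the stated 2.5% and 80%. It is the Simon optimal design with boundaries 7/14 and 23/40 on the scale of patients free of a critical AE.
- c1 = 7, c = 23, the rule as written for critical AEs: 0.361 and 0.950. It does not reproduce the stated figures. That is a separate problem and does not affect this point.

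**3. Weight of one patient**

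One patient in 40 is 1/40 = 2.5 points. The whole design contrast is 56 − 32.5 = 23.5 points.

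**4. Illustration of sensitivity (assumed shares)**

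Suppose the 56% includes laboratory events that this trial would not report, and the true rate is 56%. Let m be the share of patients whose only critical event is such an unreported value. The observed rate is then p = 0.56 − m.

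| m (patients of 40) | Chance of rejecting, 6/14 and 16/40 | Chance of rejecting, 7/14 and 23/40 |
|---|---|---|
| 0 (0) | 2.4% | 36.1% |
| 2.5 points (1) | 4.8% | 45.3% |
| 5 points (2) | 8.7% | 54.3% |
| 10 points (4) | 22.5% | 70.5% |

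The documents give no value for m. They also do not say how laboratory events were ascertained for the 56%. The table shows how sensitive the decision would be under the supposition; it does not estimate an actual error.

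**The case against.** The other side has a good deal to say, and most of it stands as a limit on the point.

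- **The relevance rule is not free judgement.** Protocol 7.2.1 names withdrawal, treatment and manifestations, and judgement is the residual route. For patients with baseline values up to 3 × ULN, Protocol 6.1.4.4 attaches treatment interruption and dose reduction to grade 3 or higher ALT, AST or bilirubin, which are visible actions. This stands, although interruption is not among the examples of relevance in 7.2.1.
- **Laboratory data are not reduced to means.** SAP 8.6.1 also gives minimum, quartiles and maximum, so an extreme scheduled value is visible, and the individual data are listed. This stands, but neither gives a rate of affected patients.
- **A test prompted by an AE concerns an event that may already be in the AE tables.** This stands. A reader might infer from the 28-day visit spacing after cycle 2 that most short laboratory excursions never reach any summary. The documents do not support that: they give no episode durations, visits are closer in cycles 1-2, and a reported episode is in the AE tables.
- **Protocol 7.2.3 is not a second filter.** A reader might take "CTC Grade 4 lab abnormalities will be documented in the laboratory data and will be reviewed on a regular basis" to exempt grade 4 values from AE reporting. The passage concerns SAE notification only.
- **The protocol's laboratory toxicity rates do not measure what is missed.** Grade 3 AST/ALT at 11% in the phase 3 trial, and grade 3 or higher thrombocytopenia at 17% and AST at 12% in the phase 2 study, are AE rates that were reported. The phase 2 study also started at 100 mg/day, against 60 mg/day here.

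The objection does not remove the central fact: no planned output counts patients by laboratory-derived grade, and unscheduled values are excluded from the summaries by rule.

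**Conclusion.** The point holds as a gap in the safety analysis that is cheap to close. Graded laboratory toxicity enters the results only through reported AEs, under two protocol definitions that differ. The summaries that could check that reporting are ungraded and leave out unscheduled values.

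Its size cannot be fixed from the documents. Each patient whose only critical event is an unreported laboratory value moves the rate by 2.5 points, but the number of such patients is unknown. A reader might conclude that the plan understates toxicity against the 56%. That does not follow, because the ascertainment of laboratory events behind the 56% is not described and the direction of any bias is therefore open. Listing unscheduled values also cannot in itself change the primary rate, which counts AEs.

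The same argument should not be extended to QTcF. Protocol 7.2.6.3 puts the overall ECG interpretation and diagnosis in the eCRF, and does not show that QTcF values are recorded there.

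**What to change.** 1. **SAP 8.6.1 and 8.6.5.3.** Derive CTCAE v5.0 grades from all available post-baseline laboratory values, scheduled and unscheduled, up to 30 days after the last dose, using local reference ranges. Present shift tables from baseline to worst grade. The baseline matters because patients may enter with AST/ALT up to 5 × ULN. Include unscheduled laboratory and blood pressure values in worst-value summaries.
2. **SAP 8.6.5.1.** Add one supportive critical-AE rate, with exact confidence interval, that also counts new laboratory-derived events of grade 3 or higher. Keep the reported-AE rate as the outcome to which the two-stage rule applies.
3. **Protocol 7.2.1 and 8.1.1.** Reconcile when a laboratory abnormality is an AE.

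**Cost.** SAP wording, a few extra tables and no new visits. Analyses are done locally (Protocol 7.2.6.4), so site reference ranges are needed, and the documents do not say that these are collected. After the end-of-treatment visit, laboratory tests are at the investigator's discretion, so coverage to 30 days will be incomplete. The supportive rate can only equal or exceed the reported-AE rate and is less comparable with the 56%, which is why it should stay supportive.

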8.6.2 Specific Descriptive Analysis

For the binary variables related to the primary and secondary outcomes, the estimation of rates and 95% CI will be performed by means of Clopper-Pearson exact method.

The Kaplan-Meier method will be used to describe the time to event endpoints, the median and their 95% CI. Analysis will follow censoring rules as described in section 8.5.1.

The continuous efficacy variable recruited by time-point will be analysed as a descriptively by means of the MMRM approach, fitting time-point as a fixed effect, and the subject and error terms as random. The dependent variable will be the absolute values (or absolute change from baseline when applicable). The within-patient variance-covariance matrix will be assumed to be unstructured. If this analysis fails to converge, the following structures will be tested in the following order until convergence: AR(1) (Auto-Regressive first order), Toeplitz and CS (Compound Symmetry). Time-point effects have been estimated by means of Least Square Means (LSM) and their standard error (SE) and 95% CI. Time-course evolutions have been estimated by LSM and their SE and 95%CI. The same analysis with a previous rank transformation applies to ordinal variables.

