Primary endpoints		
Any AEs Related-AEs Rate of death AEs leading to treatment discontinuation Serious AEs (SAEs) Rate of AEs (CTCAE)≥3 excluding palmar-plantar erythrodysthesia	Treatment policy	None
Secondary endpoints		
ORR (main secondary outcome)	Treatment policy	While on treatment*
Overall survival (OS)		
Time to progression (TTP)		
Pattern of progression	Treatment policy	None
Rate of patients who develop new extra-hepatic spread		
Post-progression survival (PPS)		

*(censored after treatment ICEs)

The ORR rate will be handled using the Treatment Policy strategy. In the unexpected case of missing due to no radiologic assessment was conducted, the composite strategy will be applied by imputing to ORR to failure.

No formal imputations will be performed for any other variable. For the categorical variables the analyses will be based on the Available Data Only (ADO) approach. With regards to the continuous variables, mixed models^{15,16,17} are robust to the presence of missing at random (MAR) and conducts the analysis with all participants despite the presence of missingness. Of note, this method calculates the estimations based on the variance-covariance structure but without any formal imputations.

No formal imputation will be used for dates due to all post-inclusion dates are complete date.

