8.6.3 Definitions and derivation of data

The following definitions and derivations will be used for this study:

- The analyses will be performed by visits and the baseline values for the calculation of the differences (absolute or relative) with respect to the baseline using the following strategy:
 - Baseline values will be defined as the last measurement taken before the first administration.

- The value of the baseline visit in case of measurement existing in that visit.
- The value of the screening visit if there is no measurement in the baseline visit.
- Start of the treatment period will be defined as the date of inclusion
- Absolute differences from baseline for each visit:
 - Absolute differences = observed value - baseline value
- Relative differences from baseline (only for the size or tumour):
 - Relative difference = [observed value-baseline value] / baseline value

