8.6.5.3.1 Tumor size

The tumor size of target lesions (absolute values, absolute difference and relative differences) will be described by time-point.

Also the absolute values and absolute differences will be analysed by means of MMRM model specified in section 8.6.2.

The relative change in tumor size will be plotted by means of Spider plot and the best change in the tumor size using a waterfall plot.

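### The change-from-baseline MMRM leaves the baseline value out, so it drops patients with no later value and is biased if dropout depends on baseline; report change as a contrast from the absolute-value MMRM instead

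*SAP*

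**What the plan says.** SAP 8.6.2 describes the MMRM for continuous variables as "fitting time-point as a fixed effect, and the subject and error terms as random". It adds: "The within-patient variance-covariance matrix will be assumed to be unstructured", with AR(1), Toeplitz and compound symmetry as fallbacks. On the outcome it says: "The dependent variable will be the absolute values (or absolute change from baseline when applicable"). No section names the baseline value as a covariate, and none says whether the baseline visit is a time-point in the absolute-value model.

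SAP 8.6.3 defines change as "Absolute differences = observed value - baseline value", so a change exists only where a later value exists.

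The model is used on both scales. For laboratory values, vital signs and the other continuous variables of 8.4.2, SAP 8.6.5.3 says these are "recruited by time (absolute values and absolute differences when applicable) will be analyzed by means of MMRM model specified in section 8.6.2". For tumour size, 8.6.5.3.1 says: "Also the absolute values and absolute differences will be analysed by means of MMRM model specified in section 8.6.2". The quality-of-life subsections say only that the MMRM will be applied and do not name change scores.

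On missing data, SAP 8.5 says that mixed models "are robust to the presence of missing at random (MAR) and conducts the analysis with all participants despite the presence of missingness". SAP 8.1 and 8.6 use the Safety set, which is eligible patients with at least one dose, for every analysis.

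**The concern.** An MMRM is valid under MAR because the observed values that predict dropout are in the likelihood. In the change model the baseline is neither a response nor a covariate; it enters only inside the difference. Two things follow. A dosed patient with a baseline and no later value supplies no row. And if patients with a poor baseline leave sooner, those who remain started better than average and regress towards the mean. The model counts that regression as change.

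The sign depends on the scale. Where higher is better, the result is a spurious decline; where higher means sicker, it is a spurious rise. The trial has no control arm in which a shared bias would cancel. SAP 7.2.1 ends treatment for symptomatic progression, toxicity, patient decision or death, so a link between illness and leaving is plausible, although the documents do not quantify it.

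**Working it through.** The documents give no SD, within-patient correlation or dropout rate for these variables, so the plan has no figure to reproduce.

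**Inputs from the documents.** N = 40 (SAP 7.4). Quality of life is taken at Day 1 of Cycles 1 and 3, then every 3 cycles, and at end of treatment (EOT) (SAP 7.7, note 11). This puts the first three later visits at C3, C6 and C9.

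**Assumed inputs.** SD 20, true change 0, higher is better, exchangeable correlation ρ of 0.4 to 0.7, log-odds of staying rising by 0.5 to 1.0 per SD of baseline, and 30, 22 and 17 of 40 patients remaining at the three visits.

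**Step 1: source of the bias.** Let Y₀ be the baseline value with mean μ₀, D the change at a visit, and δ the true mean change. With equal SDs,

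E(D | Y₀) = δ − (1 − ρ)(Y₀ − μ₀).

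If staying depends on Y₀ and the patients in the model have baseline mean μ₀ + Δ, the first-visit bias is −(1 − ρ)Δ. It vanishes when Δ = 0 (dropout unrelated to baseline) and shrinks as ρ approaches 1. In a separate simulation (ρ = 0.5, slope 1.0, 73% with a first later value), Δ was 0.226 SD. Then −(1 − 0.5) × 0.226 = −0.113 SD, or −2.3 points at SD 20. Further selection after the first visit takes the last-visit bias to −0.184 SD (−0.184 × 20 = −3.7 points).

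**Step 2: third-visit bias at N = 40.** Maximum likelihood with unstructured covariance. EOT is treated as one more time-point, available for every patient or for a random 75%; the SAP does not say how EOT enters the model.

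| EOT questionnaire | Patients absent from change model | Bias of change model, points |
|---|---|---|
| Complete | 0 | −0.8 to −2.8 |
| 75% complete | 10 × 0.25 = 2.5, so 2–3 | −0.9 to −3.2 |
| Not used | 40 − 30 = 10 | −1.3 to −4.6 |

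The small end of each range is ρ = 0.7 with log-odds 0.5; the large end is ρ = 0.4 with log-odds 1.0. The visit-minus-baseline contrast from the absolute-value model, with baseline as first time-point, stays within 0.05 points throughout.

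**Step 3: limits.** With dropout unrelated to the outcome, both estimates are unbiased. At ρ = 0.95 the change-model bias is 0.1 to 0.4 points in size. With correlation that decays over time (AR(1), ρ = 0.5, slope 1.0) and no EOT value, it reached −0.35 SD.

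**Step 4: is a baseline covariate enough?** With LS means taken at the included patients' baseline mean, it removes only about 36% to 52% of the bias. The remainder is again −(1 − ρ)Δ: in the Step 1 example it was −0.113 SD. With baseline, its interaction with time-point, and LS means at the baseline mean of all dosed patients, the bias falls within 0.05 points.

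**The case against.** **EOT assessment.** A reader who looks only at C3, C6 and C9 might infer that about 10 of 40 patients vanish from the quality-of-life change model. The schedule does not support that: a patient who stops before C3 is still due an EOT questionnaire. Laboratory tests and vital signs are also taken at Day 15 of Cycles 1 and 2 and at EOT, so few patients would lack a later value there. This stands, and it reduces the size of the bias without removing it.

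**Conditionality.** A reader might also infer that the model is biased as a matter of fact and will report a decline that did not happen. The documents give nothing to establish that. It needs dropout related to the baseline of the same variable and a within-patient correlation that is not very high. Tumour size may track closely within patients, in which case the bias there would be small.

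**The sound analysis is nearly in the plan.** The absolute-value MMRM is already specified, and SAP 8.5's description of it ("conducts the analysis with all participants despite the presence of missingness") can be true for that model. But this requires baseline to be one of its time-points, which the SAP does not state. The plan also commits to the change-scale model for tumour size and, where applicable, for other variables.

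**Low stakes.** SAP 8.6 calls the analyses non-inferential, quality of life is exploratory (SAP 6.3), and 8.6.1 tabulates N and differences by time-point, so attrition will be visible. This stands and limits the severity. Visible attrition does not, however, correct the estimate.

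**Conclusion.** The point holds in conditional form. The change-scale MMRM, as specified, leaves out dosed patients with no later value and is biased when dropout depends on the baseline level of the variable analysed. SAP 8.5's claim does not hold for that scale.

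The sizes in the working are illustrations: they rest on the assumed SD, correlation and dropout strength. With EOT complete no patient is lost, and the third-visit bias is below 3 points on an SD of 20.

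Only descriptive continuous outcomes are touched: laboratory values, vital signs, tumour size, and quality-of-life scores where they are analysed as change. AE rates, ORR, OS and TTP are unaffected. It would be wrong to infer that the trial's main conclusions are at risk, or that an apparent worsening must be an artefact. This is a minor improvement that is worth making because it is cheap.

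**What to change.** In SAP 8.6.2, state that the baseline visit is the first time-point of the absolute-value MMRM. Report mean change at each visit as the LS-mean contrast, visit minus baseline, with its 95% CI from that model. Drop the separate change-score MMRM, and align 8.6.5.3 and 8.6.5.3.1.

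If the change model is kept, add the baseline value and its interaction with time-point, and evaluate LS means at the baseline mean of all dosed patients. This removes the bias, but its CI treats that mean as known, so it is not fully equivalent to the contrast.

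The cost is a sentence in the SAP, with no new data. Intervals at late visits become somewhat wider when dropout depends on baseline. In the simulation without EOT, the third-visit SE rose by between 3% (5.30 against 5.14) and 24% (5.26 against 4.23). When dropout is unrelated to baseline, the two approaches are about equally precise.
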